2. MATERIALS

Participants

The sample size will be 16 participants per group (2 groups) that attend 8 treatment sessions.

Inclusion criteria

Male or females between 18 and 65 years of age diagnosed with disordered gambling based on the Problem Gambling Severity Index (PGSI) who can speak and read English, capable of giving informed consent, and don't have any of the exclusion criteria.

Minimum Age: 18 Years

Sex: All

Gender Based: No

Accepts Healthy Volunteers: No

Exclusion criteria

- a. History or evidence of chronic or residual neurological disease.
- b. A pacemaker or deep brain stimulation.
- c. Metal implants in head or neck area (e.g. postoperative clips after intracerebral aneurysm; arterial aneurysm in the vascular system, implantation of an artificial hearing aid).
- d. Intracerebral ischemia/history of bleeding.
- e. Prior evidence of epileptic seizures, history of epilepsy.
- f. History of head injury with loss of consciousness.
- g. Any serious medical conditions (disease of the internal organs).
- h. Pregnancy or breast-feeding.
- i. Negative screening from the clinic psychiatrist

Software

This research uses a CE marked medical device, transcranial direct current stimulation (tDCS) built in the international company Neuroelectrics (<https://www.neuroelectrics.com/products/>). Specifically, Starstim® is a wireless hybrid EEG/tCS neurostimulator system. It includes the comfortable neoprene head cap where the electrodes can be easily inserted. Starstim® complies with the European legislation for clinical research.

Cognitive and physiological measurement tools

Primary outcomes:

1. Yale-Brown Obsessive Compulsive Scale adapted for Pathological Gambling (PG-YBOCS): it is a 10-item questionnaire that measures the gambling severity. The scores range from 0 to 4. The questions 1 to 5 assess urges and thoughts associated with gambling disorder, and the rest of the questions assess the behavioural component of the disorder in the past week. The total score will be calculated as well as the separate scores. Gambling severity will be higher with higher scores (we will obtain measures of PG-YBOCS in all sessions 1,2,3,4,5,6,7 and 8).
2. Visual Analogue Scale (VAS) for gambling cravings: it is a horizontal line which length is 100 mm where the left side corresponds to the lower score and the right side to the highest score (it ranges from 0 to 10). The participant will draw a line starting from the lowest level to the level that better represents their gambling cravings at the current time. The score will be calculated by measuring this line (in millimetres). The gambling cravings will be higher with higher VAS scores (we will obtain measures of VAS in all sessions 1,2,3,4,5,6,7 and 8).
3. Gambling Symptom Assessment Scale (G-SAS): it is a 12-item scale to measure gambling symptoms. Each of the 12 questions has a score ranging from 0 to 4 based on the last week, which makes it useful to measure changes during treatment. The total score ranges from 0 to 48. The symptoms severity will be higher with higher G-SAS scores.
4. Cambridge Gambling Task (CGT): it is a cognitive task that dissociates risk taking from impulsivity, because in the ascending bet condition the participant who wants to make a risky bet has to wait patiently for it to appear (10 minutes). <http://www.cambridgecognition.com/cantab/cognitive-tests/executive-function/cambridge-gambling-task-cgt/>

Secondary outcomes:

1. Information Sampling Task (IST): it tests impulsivity and decision making. The participant is instructed that they are playing a game for points, which they can win by making a correct decision (up to 15 minutes). <http://www.cambridgecognition.com/cantab/cognitive-tests/information-sampling-task-ist/>
2. The Stop Signal Task (SST): it measures response inhibition or impulse control (up to 20 minutes). <http://www.cambridgecognition.com/cantab/cognitive-tests/executive-function/stop-signal-task-sst/>
3. Encephalography (EEG) activity: EEG resting state oscillatory neural activity will be obtained before and after tDCS stimulation to study the correlation of tDCS effects and neurophysiological changes in the brain.

Trial design

- Study Type: Interventional
- Primary Purpose: Treatment
- Framework: Superiority (Treatment will be superior to placebo (sham condition)).
- Interventional Study Model: Parallel Assignment. Investigation of the effects of transcranial direct current stimulation (tDCS) in combination with cognitive behavioural therapy (CBT) against the effects of CBT alone.
- Number of Arms: 2
- Masking: Double (Participant and Operator) Participants will be allocated either to a tDCS Stimulation condition or to a tDCS Sham condition.
- Allocation: Randomized

Trial setting

The trial will run at The UK National Problem Gambling Clinic (NPGC), in London. This is a single centre and it consists on an educational project and therefore a non-commercial trial.

There are not specific requirements to run the trial or different types of site. All participants will be recruited at the NPGC through members of the staff when potential participants contact the clinic to receive treatment for gambling disorder.

Patients that contact with the health care team at the NPGC will be offered the opportunity to participate voluntarily in the research. If they are interested they will need to confirm that they meet the inclusion criteria of the study which appears in the invitation letter and will be given the researcher contact details to obtain more information about the trial.

Trial procedures

The intensity for neuromodulation will remain constant across all groups at 1.8 milliamps (mA), which is a standard intensity for induced cognitive change in the tDCS literature. In the sham condition, participants will experience only 60 seconds of tDCS stimulation with 1.8 mA intensity (30 seconds ramp up and 30 seconds ramp down), which is enough to induce a tingling sensation that is associated with tDCS neuromodulation but at the same time this is not enough to alter neural activity and the left 19 minutes of the tDCS intervention they will receive 0 mA intensity. Electroencephalography (EEG) resting state oscillatory activity will be recorded during 5 minutes before and 5 minutes after tDCS.

Participants will be randomly allocated either to a real stimulation condition or to a control condition (sham). Each participant will attend to a 20 minutes transcranial direct current stimulation (tDCS) weekly session for 8 consecutive weeks (8 sessions). During the sessions they will complete cognitive tasks and questionnaires for a total time of 1 hour to assess individual characteristics (e.g. impulsivity, risk-taking behaviour) and where EEG resting state will be recorded to inform about the neurophysiology of tDCS effects in task performance.

The participant will complete:

- The consent form
- A series of questionnaires to assess cravings, addiction severity and gambling symptoms.

Consecutively, the researcher will set up of equipment and parameters (place the cap on the participant's head); apply tDCS stimulation (20 minutes) while participant complete cognitive computer based tasks; remove the cap to conclude the session.

- In session 1 and session 8 participant will complete the next questionnaires and cognitive task before the tDCS/EEG protocol:
 1. Gambling Severity Symptom Assessment Scale (G-SAS).
 2. Cambridge Gambling Task (CGT).
- In sessions 1, 2, 3, 4, 5, 6, 7 and 8 participants will complete the next questionnaires and cognitive tasks (tests 1-3 before tDCS/EEG protocol and task 4 during tDCS stimulation). EEG resting state will be recorded before and after tDCS:
 1. Yale-Brown Obsessive Compulsive Scale adapted for Pathological Gambling (PG-YBOCS)
 2. Visual Analogue Scale (VAS) for gambling cravings.
 3. Information Sampling Task (IST)
 4. Stop Signal Task (SST)
 5. EEG resting state recording

Randomization method

Simple randomization will be employed. This method is based on a single sequence of random assignments. Computer-generated random numbers will be used for simple randomization of subjects prior to the experiment start – assigning randomised numbers to the order in which participants sign up - to ensure equivalent numbers of participants per arm. This technique guarantees randomness of the assignment of a subject to a particular group.

Masking

Neuroelectrics tDCS software will be set up in double blind mode, which ensures that neither the investigator (who conducts the experimental session) nor the participant, will know the condition (real stimulation or sham) the participant has been allocated to. Participant allocation to each stimulation group will be randomized prior the study commences as stated above, and tDCS templates will be created for each participant, to ensure that they will remain during the 8 stimulation sessions in the same group.

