1. PROCEDURE

The research consists on studying the effects of tDCS in combination with cognitive behavioural therapy (CBT) in adults diagnosed with gambling disorder that attend the UK National Problem Gambling Clinic. The design of the study consists on a double blind randomized control interventional trial with parallel assignment (two interventions – tDCS in combination with CBT that will be evaluated against CBT alone).

Participants will be split in two groups depending on the treatment they receive. The treatment groups will be: tDCS real stimulation with CBT or tDCS sham with CBT. Real stimulation condition involves the application of tDCS stimulation for 20 minutes whereas sham condition is used as a control (similar to a placebo).

The investigators aim to have a total of 32 participants diagnosed with gambling disorder based on the Problem Gambling Severity Index (PGSI). There will be 16 participants per condition, having two conditions (real stimulation and sham).

Treatment 1. Participants will attend 8 weekly sessions where they receive tDCS real stimulation while complete CANTAB cognitive tasks to measure cognitive functions and following this, they will attend a CBT session.

Treatment 2. Participants will attend 8 weekly sessions where they receive sham tDCS, while complete CANTAB cognitive tasks to measure cognitive functions and following this, they will attend a CBT session.

Primary endpoint/outcomes

1. Change in scores on the Yale-Brown Obsessive Compulsive Scale adapted for Pathological Gambling (PG-YBOCS). [Time Frame: Change from baseline PG-YBOCS scores at week 2, 3, 4, 5, 6, 7 and 8].
2. Change in scores on the Visual Analogue Scale (VAS). [Time Frame: Change from baseline VAS scores at week 2, 3, 4, 5, 6, 7 and 8].
3. Change in scores on the Gambling Symptom Assessment Scale (G-SAS). [Time Frame: Change from baseline G-SAS scores at week 8].
4. Change in scores on the Cambridge Gambling Task (CGT). [Time Frame: Change from baseline CGT scores at week 8].

Secondary endpoints/outcomes

1. Change in scores on the Information Sampling Task (IST). [Time Frame: Change from baseline IST scores at week 2, 3, 4, 5, 6, 7 and 8].

2. Change in scores on the Stop Signal Task (SST). [Time Frame: Change from baseline IST scores at week 2, 3, 4, 5, 6, 7 and 8].
3. Changes in encephalography (EEG) neural oscillatory activity. [Time Frame: Correlation of tDCS and EEG activity in weeks 1, 2, 3, 4, 5, 6, 7 and 8].

Primary objective

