The main objective is to study whether 8 weekly sessions during 8 consecutive weeks of tDCS simulation will help to decrease cravings and addiction symptoms such as risk-taking behaviour and impulsivity in patients diagnosed with gambling disorder attending the UK National Problem Gambling Clinic, exploring whether tDCS combined with CBT will improve the treatment outcomes – reducing significantly more the symptomatology, compared to CBT treatment alone.

Hypothesis 1:

Null hypothesis (H_0): The primary outcome measures results will be the same in the group of participants that receive tDCS real stimulation combined with CBT and the control group (sham tDCS + CBT).

Alternative hypothesis (H_A): The primary outcome measures results will not be the same in the group of participants that receive tDCS real stimulation combined with CBT and the control group (sham stimulation + CBT).

Hypothesis 2:

H_0 : The primary outcome measures results obtained in the baseline will be the same to the outcome measures results at the end of the treatment.

H_A : The primary outcome measures results obtained in the baseline will not be the same to the outcome measures results at the end of the treatment.

Secondary objectives

To investigate if electrophysiological measures (EEG resting state) predict behavioural outcomes obtained from the cognitive task performance during tDCS experiments, as well as studying the task performance progression comparing every week's results to the baseline.

Hypothesis 1:

H_0 : The secondary outcome measures results obtained from the EEG resting state will be the same in the group of participants that receive tDCS real stimulation combined with CBT and the control group (sham tDCS + CBT).

H_A : The secondary outcome measures results obtained from the EEG resting state will not be the same in the group of participants that receive tDCS real stimulation combined with CBT and the control group (sham tDCS + CBT).

Hypothesis 2:

H_0 : The secondary outcome measures results obtained in the baseline will be the same to the outcome measures results at the end of the treatment.

H_A : The secondary outcome measures results obtained in the baseline will not be the same to the outcome measures results at the end of the treatment.

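### The week-8 primary outcomes are taken before the eighth tDCS and CBT session, so they follow seven sessions, while the objective and Hypothesis 2 refer to eight sessions and the end of treatment

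*Combined protocol and SAP*

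**What the plan says.** **Aim.** Section 1, Primary objective, asks "whether 8 weekly sessions during 8 consecutive weeks of tDCS simulation will help to decrease cravings and addiction symptoms". The alternative under primary Hypothesis 2 is that the baseline results "will not be the same to the outcome measures results at the end of the treatment".

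**Endpoints.** Section 1, Primary endpoint/outcomes, measures PG-YBOCS and VAS as change from baseline at weeks 2 to 8. G-SAS and CGT are measured at week 8 only; the G-SAS time frame reads "Change from baseline G-SAS scores at week 8".

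**Timing within a session.** Section 2, Trial procedures, has two bullets. The one for G-SAS and CGT reads "In session 1 and session 8 participant will complete the next questionnaires and cognitive task before the tDCS/EEG protocol". The one for the measures taken at every session reads "tests 1-3 before tDCS/EEG protocol and task 4 during tDCS stimulation"; PG-YBOCS is item 1 of that list and VAS is item 2.

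**Order of treatment.** In both arms, section 1 describes tDCS (real or sham) with the cognitive tasks, and then "following this, they will attend a CBT session". Section 5, Analysis sets/Subgroups, gives the same order.

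**Number of assessments.** Section 5, Data source, counts two time points for G-SAS and CGT and eight for PG-YBOCS and VAS.

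**Recall.** Section 2 bases G-SAS on the last week and attaches a past-week window to the behavioural items of PG-YBOCS. VAS records craving at the moment of completion.

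**The concern.** An assessment made at the start of a session cannot reflect what is delivered later in that session. If this holds for every primary outcome at the last visit, and no later visit exists, the eighth tDCS and CBT session contributes nothing to any primary endpoint. The plan would then attribute to a completed eight-session course a result that its schedule cannot observe. The comparison of baseline with the end of treatment would in fact be a comparison of baseline with a point one session short of it. What is at stake is what the trial may claim, not whether the randomised comparison is sound.

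**Working it through.** The plan gives no alpha, power, effect size, standard deviation or dose-response, so there is no power figure of its own to reproduce. The check is a count.

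**1. Reproduce the plan's time points.** G-SAS and CGT: baseline + week 8 = 1 + 1 = 2. PG-YBOCS and VAS: baseline + weeks 2 to 8 = 1 + 7 = 8. Both match section 5, Data source. Sessions 1 and 8, or sessions 1 to 8, use up every time point, so none is left for an assessment after session 8.

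**2. Place each primary outcome within session 8.**

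| Primary outcome | Sessions | Position | Period described |
|---|---|---|---|
| PG-YBOCS | 1 to 8 | before tDCS | past week (stated for the behavioural items) |
| VAS | 1 to 8 | before tDCS | current moment |
| G-SAS | 1 and 8 | before tDCS | last week |
| CGT | 1 and 8 | before tDCS | task performance on the day |

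CBT follows tDCS, so all four also precede the eighth CBT session.

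**3. Count completed sessions.** A pre-stimulation value at session k follows k − 1 completed sessions. For k = 1 to 8 this gives 0, 1, 2, 3, 4, 5, 6, 7. The session-1 value is a proper untreated baseline. The session-8 value follows 7 of 8 sessions: 7/8 = 87.5%, leaving 1/8 = 12.5% of the course unobserved.

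**4. Recall.** Sessions are weekly, so session 8 falls about 7 days after session 7. At session 8, G-SAS and the behavioural items of PG-YBOCS therefore describe the week after session 7.

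**5. Possible size.** Let D be the between-arm difference after the full course.
- If the effect has levelled off by session 7 (assumption), the measured difference is D and the shortfall is 0.
- If the effect builds by equal steps per session (assumption), the measured difference is 7/8 × D = 0.875 D and the shortfall is 0.125 D.

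The documents do not say which of these, or what other pattern, applies.

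**The case against.** The best defence is that assessing before stimulation is good practice here. It matches the session-1 baseline, which has to come first, and it keeps acute stimulation effects out of VAS. With a one-week recall, G-SAS could not have captured session 8 on the same day anyway. All of this stands. The difficulty is the lack of a later assessment, not the position of the existing one.

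It can also be said that the endpoints are defined by week and not by number of sessions, and that the end of treatment could mean the final treatment visit. The endpoint list and the schedule do agree with each other. But the objective names eight sessions, and on the looser reading Hypothesis 2 would still use a value taken before that visit's treatment.

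Other wording in sections 1 and 2 has computer tasks done during stimulation, which might be thought to cover CGT. The itemised schedule puts CGT before tDCS. Even on the other reading CGT would precede the eighth CBT session, and the three questionnaires are unaffected.

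Three stronger readings are tempting but are not supported:
- *The arm difference is understated because the plan presumes accumulation.* Section 5, Statistical Procedures, mentions accumulative effects only in its paragraph on the secondary measures, as something to explore. It says nothing of the kind about the primary outcomes.
- *The trial loses a known amount of power.* Under linear build-up, with 16 per arm and a two-sided 5% t-test, a full-course standardised difference of 1.0 would be seen as 0.875 and power would fall from 78% to 67%. The effect size, the build-up and the test are all assumed; the planned analysis is a mixed ANOVA.
- *All of PG-YBOCS looks back one week.* As worded, the window is attached only to the behavioural items.

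**Conclusion.** The mismatch is real and follows from the schedule alone. Every primary value at week 8 comes after seven of the eight tDCS and CBT sessions, and neither an eight-session effect nor a value after treatment has ended is observed on any primary outcome.

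The between-arm comparison is not biased by this, because both arms are assessed at the same point. A reader might infer that the primary result is invalid; it is not. It is a valid estimate of the effect after seven sessions.

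How far that differs from the full-course effect cannot be determined from the documents. The two cases worked above give a shortfall of nil and of one eighth, and both rest on assumptions about how the effect builds. The need to correct the wording does not depend on which is true. This should be corrected, since it changes what the trial can conclude and the correction is cheap.

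**What to change.** **Minimum.** Restate the objective, Hypothesis 2 and the week-8 time frames as the effect after seven completed sessions, assessed at the start of the eighth, and remove the reference to the end of treatment. This is a change of wording only; its price is a slightly narrower claim.

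**Preferred, in addition.** Have participants self-complete PG-YBOCS, G-SAS and VAS once, about 7 days after session 8, with no clinic visit. In the SAP:
- name these as the end-of-treatment values;
- keep the session-8 values as the week-8 time point, described as following seven sessions;
- state how the extra time point enters the ANOVA (three time points for G-SAS, nine for PG-YBOCS and VAS) and which contrast addresses Hypothesis 2;
- state that CGT remains a measure after seven sessions;
- add a rule for forms not returned, because the present missing-value rules deal with failed tasks and skipped questions.

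**Cost.** A protocol amendment and one short set of forms for each of 32 participants. Some forms will not come back, and the researcher's completeness check before the participant leaves is lost. The setting also changes from baseline, which matters most for VAS because it records momentary craving on a measured line.

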3. ETHICAL CONSIDERATIONS

Ethical approval to conduct the study was obtained from the University Research Ethics Committee (UREC) at the University of East London and from the Health Research Authority (HRA) and will be conducted with Central and North West London (CNWL) NHS trust. Potential risks associated with tDCS are minor discomfort from wearing the tDCS electrode net and minor itchiness that immediately cease after stimulation, this is explained to the participants prior to starting. Participants will be reminded that they could stop the experiment at any time they wish, if they felt too much discomfort or distress.

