5. STATISTICAL ANALYSIS PLAN

Data source

Behavioural data sets will be obtained from computer-based cognitive tasks and questionnaires that participants complete during the stimulation sessions. The results obtained from completing these tasks and questionnaires generate measures for addiction-related symptoms such as cravings, impulsivity, risk-taking behaviour, delay aversion and control inhibition. Each participant will produce data at two time points for G-SAS and CGT measures and at eight time points for VAS, PG-BOCS and secondary measures. Electroencephalography (EEG) resting state neural oscillatory activity will be recorded for 5 minutes prior and 5 minutes after the tDCS intervention.

Analysis objectives

The investigators will study whether the behavioural and cognitive data obtained from participants in different time points are significantly different between the two treatment groups. In addition, the investigators will investigate if electrophysiological measures (EEG resting state) predict behavioural outcomes obtained from the cognitive task performance during tDCS experiments, as well as studying the task performance progression comparing every week's results to the baseline.

Analysis sets/Subgroups

The following data sets subgroups will be analysed:

1. Experimental - Stimulation with CBT: Participants that attend to 8 weekly sessions of tDCS stimulation and that following the tDCS session, they attend to a cognitive behavioural therapy (CBT) session.
2. Sham Comparator - Sham with CBT: Participants that attend to 8 weekly sessions of sham tDCS and that following the tDCS session, they attend to a CBT session.

The aim is to study whether the combination of stimulation and therapy help to improve the treatment outcomes in comparison with CBT alone.

Variables and covariates

Primary Dependent Variables:

1. Pathological Gambling adapted Yale-Brown Obsessive Compulsive Scale (PG-YBOCS) scores for gambling severity.
2. Visual Analog Scale (VAS) scores for gambling cravings.
3. Gambling Severity Symptoms Assessment (G-SAS) for gambling symptoms.
4. Cambridge Gambling Task's (CGT) scores for gambling behaviour.

Secondary Dependent Variables:

1. Stop signal task's (SST) scores for inhibition control.
2. Information Sampling Task's (IST) scores for impulsivity.
3. EEG resting state oscillatory neural activity.

Independent Variables:

1. tDCS condition (Stimulation or Sham)
2. Time (sessions 1 to 8)

Covariates:

1. Age
2. Gender

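### G-SAS and CGT have their only post-baseline measurement at tDCS session 8, with no assessment for anyone who stops earlier or misses it, so the week-8 comparison is in effect limited to completers.

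*Combined protocol and SAP*

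**What the plan says.** - **Endpoint (1. Procedure, Primary endpoint/outcomes).** Both outcomes are dated by week: "Change from baseline G-SAS scores at week 8" and "Change from baseline CGT scores at week 8".
- **Collection (2. Materials, Trial procedures).** "In session 1 and session 8 participant will complete the next questionnaires and cognitive task before the tDCS/EEG protocol". PG-YBOCS and VAS are collected at every session from 1 to 8.
- **Schedule (same section).** Stimulation is planned as a "weekly session for 8 consecutive weeks (8 sessions" in all.
- **Number of values (5. Statistical Analysis Plan, Data source).** "Each participant will produce data at two time points for G-SAS and CGT measures". The time factor under Variables and covariates is expressed in sessions, not weeks.
- **Stopping (3. Ethical Considerations).** "Participants will be reminded that they could stop the experiment at any time they wish". Discomfort or distress is given as the occasion. No section describes an assessment after stopping, a visit window, or what happens to the numbering when a week is missed.
- **Analysis groups and missing data (5. Statistical Analysis Plan).** Each group is described by attendance at 8 weekly sessions. For tasks, a whole-task error is the only source of missing data foreseen, and the participant is then left out of that task's analysis. For paper questionnaires, a missing item is replaced by the value the participant chose most often elsewhere.

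**The concern.** For G-SAS and CGT the whole treatment comparison rests on one post-baseline measurement, and that measurement is tied to receiving the last tDCS session. A participant who stops stimulation after, say, session 5 contributes nothing to either outcome, even if still attending the clinic for CBT. PG-YBOCS and VAS lose their week-8 value in the same way but keep the weekly values up to stopping.

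Two things are at stake. One is precision: with 16 per arm, each lost participant is a visible share of the data. The other is selection: if people stop for reasons linked to the arm and to how they are doing, those who reach session 8 are no longer the groups that were randomised. Real stimulation lasts 20 minutes and sham delivers current for 60 seconds, so unequal stopping is possible. The documents do not show that it will happen.

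**Working it through.** There is no figure in the plan to reproduce. The sample size of 32 is stated without alpha, power, effect size, SD or dropout. The check is first a trace through the text, then three illustrations on assumed rates.

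**1. What a participant who stops before session 8 contributes**
- G-SAS and CGT: session 1 only, so no change score.
- PG-YBOCS and VAS: values up to the last session attended, nothing at week 8.
- Missing-data rules: a CGT never taken is not a task error, but the nearest rule drops the participant from that task. A G-SAS form never filled in has no answered items from which to take a most common value. A 2 x 2 mixed ANOVA on baseline and week 8 needs both values.
- Result: the participant leaves both analyses, which agrees with groups described by attendance at 8 sessions.

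**2. Loss of precision**
Inputs: 16 per arm (documents); stopping rate s, the same in both arms (assumed). The number left per arm is 16 x (1 - s).
- s = 10%: 16 x 0.90 = 14.4
- s = 20%: 16 x 0.80 = 12.8
- s = 30%: 16 x 0.70 = 11.2

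For an assumed true difference of 1.0 SD and two-sided 0.05 (noncentral t), power is 78% at 16 per arm, 72% at 14, 69% at 13 and 61% at 11.

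**3. Possible bias**
If stoppers' mean change is g SD worse than completers' in both arms, the completer contrast is shifted in favour of real tDCS by (stopping rate in real arm - stopping rate in sham arm) x g. With g = 0.5 (assumed):
- equal rates: 0 x 0.5 = 0
- 5 points apart: 0.05 x 0.5 = 0.025 SD
- 15 points apart (for example 25% against 10%): 0.15 x 0.5 = 0.075 SD

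The standard error of a two-group contrast at 16 per arm, with unit SD, is sqrt(2/16) = 0.35 SD. The largest of these shifts is 0.075 / 0.35 = about one fifth of it. If stopping were more frequent in the sham arm, the sign would reverse.

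**4. Missed weeks**
Assume that each of weeks 2 to 8 is missed independently with probability m. The result depends on a rule that the documents do not give.

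| m | Sessions roll forward: session 8 falls after week 8, 1 - (1 - m)^7 | Numbers follow the calendar: week 8 itself missed, m |
|---|---|---|
| 2% | 13% (4.2 of 32) | 2% (0.6 of 32) |
| 5% | 30% (9.7 of 32) | 5% (1.6 of 32) |
| 10% | 52% (16.7 of 32) | 10% (3.2 of 32) |

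In the middle column the value is late; in the right-hand column it is absent.

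**The case against.** The strongest reply is that week and session are the same thing in this trial. One session a week for 8 consecutive weeks makes session 8 the week-8 visit, and the protocol uses the two terms interchangeably for PG-YBOCS and VAS as well. That stands. A reader might infer that the endpoint and the collection schedule contradict each other; they do not, and they can part only after a deviation.

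A reader might also infer that anyone who misses a week loses both outcomes. That does not follow. Someone who misses week 4 still has session 8 in week 8 if numbering follows the calendar. If sessions roll forward the value is late, not lost. Loss would require keeping the dates while renumbering the visits, which no section describes. The 13% to 52% range therefore applies only to rolling forward.

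Three further objections hold in part:
- The discomfort named in the ethics section comes from the electrode net, which both arms wear, and sham is designed to tingle. Unequal stopping is possible, but no stopping rate for either arm has support in the documents, and the illustrated bias is small.
- The right stated is to stop the experiment. Some who use it will also decline assessment, and no change to the schedule recovers their data.
- It would be too strong to say that no analysis could help. Late values would exist, and weekly PG-YBOCS and VAS before stopping could inform an imputation. But that would rest on assumptions about G-SAS and CGT that the trial's own data could not check for stoppers, and the plan proposes no such analysis.

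None of this answers the central gap: a participant who stops tDCS but would still complete a questionnaire and a task is not asked to.

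**Conclusion.** The point holds as a gap in outcome collection. For two of the four primary outcomes the plan as written gives a completer-only comparison at week 8, and for the other two it loses the week-8 value of anyone who stops early. This follows from the text and needs no assumption about rates.

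Its size cannot be established, because the documents give no stopping or attendance figures. On the assumed rates above, the cost is roughly 2 to 5 participants per arm in precision, and a bias of 0 to 0.075 SD if stopping differs by up to 15 points and stoppers do 0.5 SD worse. The missing rule for skipped weeks is a lesser matter of detail. It affects timing for many participants under one reading and leaves few without a value under the other. The change is worth making because it is cheap and reduces selection, not because a large bias has been shown.

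**What to change.** 1. **2. Materials, Trial procedures.** Collect G-SAS, CGT, PG-YBOCS and VAS at week 8 counted from session 1, within a stated window, from every randomised participant who still consents to assessment, regardless of how many tDCS sessions were received. The CBT visit is one practical place.
2. **Same section, and Variables and covariates in the SAP.** Tie session numbers to calendar weeks for data collection and analysis, so that the time factor matches the endpoint definitions. This concerns the labelling of assessments only. Whether a missed stimulation session is made up is for the investigators to state.
3. **Analysis sets/Subgroups and Handling of missing values.** Describe the primary comparison as all randomised participants by allocated arm, include the week-8 values collected after stopping, and acknowledge stopping and missed sessions as sources of missing data.

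The cost is protocol wording plus, for those who have stopped, one assessment at week 8; the protocol lists the CGT at 10 minutes and the G-SAS has 12 items. Some week-8 values will be taken without a tDCS session that day, and people who leave the study entirely will still be missing.

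Weekly G-SAS is optional. The protocol says of its one-week recall, "which makes it useful to measure changes during treatment", and it would give early stoppers some post-baseline values. But it adds to a session already planned at 1 hour and does nothing for the CGT.
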